3.0 SCHEMA

- 3.1 Patients will be enrolled if they have a pathologic diagnosis of cancer along with imaging consistent with one or more brain metastases. All patients must meet all enrollment criteria.
- 3.2 Only 1 target per patient, termed the index lesion, will be enrolled and receive the investigational dose prescription. The enrolled index lesion will be the largest brain metastasis by definition. Any additional treated non-index lesion will receive a standard of care dose prescription that has previously been demonstrated to be safe.
 - 3.2.1 Therefore, each enrolled patient will be included in either the cohort of patients with an index lesion measuring 2.1-4 cm in maximum diameter or the cohort of patients with an index lesion measuring 4.1-6 cm in maximum diameter. An individual patient can only be included in 1 of the 2 cohorts as

determined by the index lesion diameter. The index lesion maximum diameter will determine the cohort and subsequent dose escalation schedule.

- 3.3 Enrolled patients will undergo appropriate MRI brain imaging that will be fused with the treatment planning CT-simulation scan for target identification.
- 3.4 Utilizing available clinical data (pathology, physical exam, MRI, and CT-simulation) physicians, medical dosimetrists, and physicists will create and approve a treatment plan if all dosimetric and quality assurance requirements are met.
- 3.5 FSRT will be delivered over 5-14 calendar days. The exact treatment schedule will be at the discretion of the treating physician.
- 3.6 Following completion of treatment, patients will be evaluated with clinical exams, imaging, and quality of life questionnaires at regular intervals.

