9.4 Follow-up

Enrolled patients will participate in a follow-up schedule as outlined in Table 8.1. Two weeks post- FSRT, the study coordinator will call the patient to assess how they are feeling and/or experiencing any toxicities. This will include a history and physical examination, performance status evaluation, MRI of the brain, and completion of the FACT-Br questionnaire at 1 month, 3 months, 6 months, and 12 months after completion of radiation treatment.

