11.0 STUDY ENDPOINTS

- 11.1 The primary endpoint of this study is to clinically assess early toxicity, specifically, to evaluate for the presence of a dose-limiting toxicity within 90 days of the initial treatment. We are interested in a risk of 20% or less.

- 11.1.1 The definition of a dose-limiting toxicity event will be the same as that used in RTOG 9005. It will be defined as an irreversible grade 3, any grade 4, or any grade 5 neurologic toxicity related to treatment that occurs within 90 days of the start of treatment. Since a patient may have more than one tumor treated the toxicity should be assigned to the tumor and not the patient if at all possible. Only 1 target per patient will receive the investigational dose prescription, and this target will be considered the index lesion. Any additional treated non-index lesion will receive a standard of care dose prescription that has previously been demonstrated to be safe.

11.2 Secondary endpoints include toxicity and efficacy assessments.

- 11.2.1 Determine the frequency and severity of acute neurologic toxicity.
- 11.2.2 Determine the frequency and severity of late neurologic toxicity.
- 11.2.3 Determine the rate of local tumor control with FSRT.
 - 11.2.3.1 The index lesion's treatment response will be assessed according to the RANO-BM criteria where a 20% increase in maximal diameter from nadir represents local tumor progression.³⁴ Additionally, the presence of more than scant tumor cells present at the time of salvage surgery will be considered a local tumor failure. An apparent increase in tumor diameter that is observed and found to subsequently decrease in size upon further imaging will be considered an effect of therapy rather than a local failure.
- 11.2.4 Determine the extent of central nervous system disease control in accordance with the Response Assessment in Neuro-Oncology (RANO) criteria for brain metastases.³⁴
- 11.2.5 Determine quality of life over time as assessed by the FACT-Br questionnaire.

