The dose escalation plan will allow enrollment of a three-patient cohort prior to the mTPI rule taking effect at the beginning of each dose level. Up to three patients can be enrolled at the beginning of each dose escalation level. Those three patients must be followed throughout the dose evaluation period (90 days). If one of those three patients develop a DLT, then cohorts of up to three additional patients may be treated at that dose level and be within the 90-day evaluation period at any given time. For example, if 1 out of the 3 patients develops a DLT, then patients 4-6 may then be enrolled. Patient 7

may be enrolled after patient 4 has been followed without toxicity for 90 days.

Dose-finding for a cohort may be stopped when one of the following criteria is met:

- The lowest dose level appears too toxic after at least 3 patients are dosed at that dose level.
- The maximum sample size in dose finding of 30 evaluable patients per cohort has been reached.
- A minimum of 10 evaluable patients have been treated at the estimated MTD.

Analysis will be descriptive and exploratory. Data will be summarized and listed by dose level. Toxicity, local tumor control local, central nervous system disease control in accordance with the Response Assessment in Neuro-Oncology (RANO) criteria for brain metastases, and QOL, will be presented in the form of patient data listings that include, but are not limited to, age, gender, dose, and tumor response at each visit. If the data permits, local tumor control rate, central nervous system disease control rate and corresponding exact confidence interval will be calculated. Additional exploratory data analysis will be performed as data permits.

Interim review of enrolled patients demonstrated that the first three patients were not evaluable at the timepoint for the primary endpoint due to systemic disease progression and/or other medical illnesses that were deemed to be unrelated to their radiation treatment. This was presented to the clinical trials monitoring committee, and it was decided that study continuation was appropriate; however, it was agreed upon that there should be enrollment of 6 patients at dose level 1 in the cohort of patients with tumors 2.1–4 cm in diameter prior to consideration of dose escalation in order to ensure safety. After this, dosing decisions will return to the originally proposed chart as displayed below.

Table 11.1 Dose Escalation rule of the modified toxicity probability interval method

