Appendix B: Response Assessment in Neuro-Oncology Brain Metastases (RANO-BM)

	Complete response	Partial response	Stable disease	Progressive disease
Target lesions	None	≥30% decrease in sum longest distance relative to baseline	<30% decrease relative to baseline but <20% increase in sum longest distance relative to nadir	≥20% increase in sum longest distance relative to nadir*
Non-target lesions	None	Stable or improved	Stable or improved	Unequivocal progressive disease*
New lesion(s)†	None	None	None	Present*
Corticosteroids	None	Stable or decreased	Stable or decreased	Not applicable‡
Clinical status	Stable or improved	Stable or improved	Stable or improved	Worse*
Requirement for response	All	All	All	Any‡

*Progression occurs when this criterion is met. †A new lesion is one that is not present on prior scans and is visible in at least two projections. If a new lesion is equivocal, for example because of its small size, continued therapy can be considered, and follow-up assessment will clarify if the new lesion is new disease. If repeat scans confirm there is definitely a new lesion, progression should be declared using the date of the initial scan showing the new lesion. For immunotherapy-based approaches, new lesions alone do not define progression. ‡Increase in corticosteroids alone will not be taken into account in determining progression in the absence of persistent clinical deterioration.

FACT-BR (Version 4)

Below is a list of statements that other people with your illness have said are important. By circling one (1) number per line, please indicate how true each statement has been for you during the past 7 days.

PHYSICAL WELL-BEING		Not at all	A little bit	Some- what	Quite a bit	Very much
GP1	I have a lack of energy.....	0	1	2	3	4
GP2	I have nausea.....	0	1	2	3	4
GP3	Because of my physical condition, I have trouble meeting the needs of my family.....	0	1	2	3	4
GP4	I have pain.....	0	1	2	3	4
GP5	I am bothered by side effects of treatment.....	0	1	2	3	4
GP6	I feel ill.....	0	1	2	3	4
GP7	I am forced to spend time in bed	0	1	2	3	4
SOCIAL/FAMILY WELL-BEING		Not at all	A little bit	Some- what	Quite a bit	Very much
GS1	I feel close to my friends	0	1	2	3	4
GS2	I get emotional support from my family.....	0	1	2	3	4
GS3	I get support from my friends	0	1	2	3	4
GS4	My family has accepted my illness.....	0	1	2	3	4
GS5	I am satisfied with family communication about my illness	0	1	2	3	4

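### Local progression is defined as a 20% increase from nadir with no minimum in millimetres and no rule for a nadir of zero, so in index lesions that shrink to about 10 mm or less a 1-2 mm reading change can count as local failure

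*Combined protocol and SAP*

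**What the plan says.** Section 11.2.3.1 defines failure of the index lesion by saying that "a 20% increase in maximal diameter from nadir represents local tumor progression". Appendix B gives the matching entry for target lesions as "≥20% increase in sum longest distance relative to nadir". Neither the sentence, the table nor its footnotes states an absolute minimum, or how renewed enhancement is counted once a lesion has disappeared.

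Three other provisions bear on the rule:

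- Section 11.2.3.1 also says: "The index lesion's treatment response will be assessed according to the RANO-BM criteria". It cites the publication; Appendix B reproduces only a summary table.
- The same section has a reversal clause: an apparent increase "found to subsequently decrease in size upon further imaging will be considered an effect of therapy rather than a local failure". It separately counts tumor found at salvage surgery, beyond a trace, as failure.
- Section 9.4 schedules brain MRI "at 1 month, 3 months, 6 months, and 12 months after completion of radiation treatment". No later scan is scheduled.

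Local control is secondary objective 1.2.3. Section 11.5 treats it descriptively: "If the data permits, local tumor control rate, central nervous system disease control rate and corresponding exact confidence interval will be calculated".

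**The concern.** A purely relative threshold shrinks in millimetres as the lesion shrinks. It is also measured from the lowest of several readings, which tends to lie below the true size when the lesion is stable. For a small residual, the change that counts as progression can be no larger than the difference between two readings of an unchanged lesion. After a nadir of zero, any measurable enhancement exceeds 20%.

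At stake is the local control rate. Lesions that are in truth controlled would be counted as failures, and the rate would be understated. With at most 30 patients per size cohort, and results listed by dose level, a few such calls move a rate visibly.

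**Working it through.** The plan states no target rate, sample size or measurement error for local control, so there is no figure of its own to reproduce.

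**Inputs from the documents.** Baseline diameter is 21-40 mm or 41-60 mm (section 3.2.1). The threshold is 20% from nadir. Scans are at baseline and 1, 3, 6 and 12 months.

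**Step 1: the threshold in millimetres.** Step = 0.20 × nadir. Nadirs of 5, 10, 20 and 30 mm give steps of 1, 2, 4 and 6 mm.

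**Step 2: how much shrinkage this needs.** Shrinkage = 1 − nadir/baseline.

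- 10 mm nadir: 1 − 10/21 = 52% to 1 − 10/60 = 83%.
- 5 mm nadir: 1 − 5/21 = 76% to 1 − 5/60 = 92%.
- At the 30% partial-response line the step is 0.20 × 0.70 × 21 = 2.9 mm to 0.20 × 0.70 × 60 = 8.4 mm.

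The 1-2 mm case therefore arises only after deep responses.

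**Step 3: false failure by month 12.** Assumptions, none of them from the documents: 30 mm baseline, truly stable residual from month 1, independent normal reading error, all four follow-up scans done. The reversal clause is applied. Monte Carlo, 400,000 lesions per setting:

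| Stable residual | SD 0.5 mm | SD 1.0 mm |
|---|---|---|
| 5 mm | 23% | 50% |
| 10 mm | 1.5% | 23% |
| 20 mm | 0% | 1.5% |

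A hand check on these figures: for one pair of readings, P(later ≥ 1.2 × earlier) = Φ(−0.2μ / (σ√2.44)), with μ the residual and σ the SD. For σ = 1.0 mm this is Φ(−0.64) = 0.261 at 5 mm, Φ(−1.28) = 0.100 at 10 mm and Φ(−2.56) = 0.0052 at 20 mm. The month-12 reading is compared with the lowest of three earlier readings, so three times these values (0.78, 0.30, 0.016) bounds the result from above. The simulated 0.50, 0.23 and 0.015 lie below the bounds.

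**Step 4: what the reversal clause leaves.** If no later reading is lower than a flagged one, the month-12 reading is also above threshold. Every false failure that survives the clause therefore stands on the month-12 scan, where no scheduled scan can undo it. The same holds for a patient's last scan: with imaging ending at month 6 and SD 1.0 mm, the rate is 41% at 5 mm and 17% at 10 mm.

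**Step 5: other error model.** In the Step 3 formula only σ/μ matters. If error is proportional to diameter, that ratio is the CV and the rate does not depend on residual size: about 1.5% at CV 5% and 23% at CV 10%.

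**Step 6: slower shrinkage and other baselines.** With half the shrinkage by month 1 and all of it by month 3, false failure at SD 0.5/1.0/1.5 mm is:

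- 21 mm baseline, 50% shrinkage: 0.7/15.6/30.1%
- 30 mm baseline, 75% shrinkage: 5.1/28.0/40.7%
- 50 mm baseline, 50% shrinkage: 0/0.1/3.1%
- 50 mm baseline, 85% shrinkage: 5.0/27.9/40.7%

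**Step 7: effect of an absolute minimum.** A working value of 5 mm governs wherever the nadir is below 5/0.20 = 25 mm. In every cell of the Step 3 table it brings false failure to 0.1% or less.

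**The case against.** The strongest reply is that section 11.2.3.1 defers to the published RANO-BM criteria, of which Appendix B is only a summary. The full criteria are not in the documents, so whether they carry a minimum cannot be settled here. This stands as a limit on the claim: nothing shows that the cited criteria lack one. It does not remove the point. The protocol's own sentence and table give a complete rule without one, and a reader following them would apply 20% alone.

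Four stronger readings are tempting, and the documents do not support them:

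- A reader might infer that every 20% increase is a failure. The reversal clause says otherwise; the gap is the increase with no later scan, or with a later scan that is stable rather than lower.
- A reader might infer that local control is necessarily biased most in the deepest responders. That follows if reading error is constant in millimetres. With proportional error the gradient disappears (Step 5), and the documents give no error model.
- A reader might infer that the dose-control relation is flattened. That needs higher dose to shrink lesions more and the error to be constant. Neither is established, no such effect has been computed, and section 11.5 plans no dose-control test.
- A reader might set the 1 mm step beside the 1 mm slice in section 6.1.1. That slice is for the planning CT; response is read on MRI.

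A minimum also has a real cost. For true regrowth first present at month 12, with SD 0.5-1.0 mm, the written rule detects 99-100% of changes from 10 to 14 mm; with a 5 mm minimum it detects 18-45%. For 5 to 8 mm the figures are 99-100% and 1-18%. With no later scheduled scan, these cases are missed rather than called later. This stands, and it is why the 20%-only rate should still be reported.

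**Conclusion.** The point holds within limits. As written, the rule lets a 1-2 mm reading change count as local failure once an index lesion has shrunk to about 10 mm or less, and it leaves a nadir of zero undefined. The reversal clause reduces the problem but cannot reach the last scan.

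The size depends on assumptions outside the documents. With constant error of 0.5-1.0 mm, false failure per lesion is substantial at a 5 mm residual, anywhere from small to substantial at 10 mm, and minor at 20 mm. With proportional error it depends on the CV alone. How far the overall rate is understated cannot be stated, because the documents do not give the share of lesions that shrink this far.

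Only the secondary, descriptive local control rate is affected. The DLT endpoint and dose escalation do not use it. The matter is still worth correcting, because following the text as it stands can miscount a stated objective and the remedy is a matter of wording.

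**What to change.** Amend section 11.2.3.1 and the target-lesion row of Appendix B so that:

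- local progression requires both an increase of 20% or more and a stated minimum absolute increase in millimetres over nadir. The value should be taken from the cited response criteria; the 5 mm used above is only a working value;
- the text says how re-appearance after a nadir of zero is counted.

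Keep the pathology and reversal clauses, and report the local control rate under the 20%-only rule as a sensitivity analysis.

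The cost is a sentence or two in each place and one extra tabulation, with no new scans. The downside is that true small regrowth first seen on the last scan, such as 10 to 14 mm, can be missed under the combined rule. The difference between the two reported rates makes visible how many lesions turn on the minimum.

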8.0 STUDY PARAMETERS

- 8.1 For the purposes of this study, acute toxicity will be defined as event(s) that occur within 90 days of the completion of radiotherapy. Acute toxicity will be determined by both intra-treatment examinations and by scheduled follow-up evaluations after the treatment has completed. Late toxicity will be defined as any toxicity occurring > 90 days after the completion of treatment.
- 8.2 Baseline evaluations of enrolled patients must occur within four weeks of study enrollment.

Table 8.1 Required study evaluations

	Baseline	2 wk. post- FSRT	1 month	3 months	6 months	12 months
History and physical exam	x		x	x	x	x
Toxicity / AE evaluation		x ¹	x	x	x	x
Performance status (KPS)	x		x	x	x	x
MRI brain (Local & CNS control per protocol/RANO-BM)	x		x	x	x	x
FACT-Br (QOL evaluation)	x		x	x	x	x

¹ A 2 week post-treatment phone call will be made to the patient to see how they are feeling and evaluate if the patient is experiencing any toxicities.

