11.5 Dose Escalation and statistical considerations

11.5.1 The modified toxicity probability interval (mTPI) method with adjustment based on observed dose limiting toxicity (DLT) rate will be employed in decision making concerning dose escalation within each cohort investigated.³⁵ The assumptions to be applied in establishing the mTPI methodology are:

- Each specific tumor size cohort exploration may include up to 30 patients for a total enrollment of up to 60 patients.
- The MTD is defined to have 0.20 probability of toxicity.
- The acceptable variance around the MTD is ± 0.05 (i.e., the region of the MTD is 15% to 25% incidence of dose limiting toxicity).

The dose assignment recommendations for cumulative number of patients are presented in Table 11.1. The size of each patient cohort during the dose escalation phase of the study will be at least 3 patients. Once the initial three evaluable patients have cleared the DLT evaluation period then an mTPI design will be used to determine whether to escalate or de-escalate the dose. Up to 10 evaluable patients may be enrolled at a specific dose prior to making a final dose escalation/de-escalation decision. If the DLT rate of the current dose does not exceed the maximum permitted toxicity rate as defined by the mTPI, then we will evaluate the next dose level. Patients not evaluable for assessment of DLT may be replaced. For any subsequent cohort of patients, the recommended dose assignment action will be based on the total number of patients with DLTs in the current and prior cohorts treated at the same dose level. For example, if a cohort of 3 patients are treated at dose level 1 for the first time and one of them experiences a DLT, then the recommended action for the next cohort of patients will be to stay at the current dose level (S); if this recommendation is accepted, then the selected dose level for the next cohort of patients will be 1; if a total of 6 additional patients are treated at dose level 1 and there are no more DLTs observed, then the cumulative number of patients treated at dose level 1 is 9, and the cumulative number of patients with DLTs at dose level 1 is 1 out of 9, thus the recommendation would be to escalate the dose for the subsequent cohort (E).

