11.6 Sample size

11.6.1 The total number of subjects enrolled in the study may vary as the study may terminate if the DLT rate exceeds the maximum permitted toxicity rate per the mTPI. Each specific tumor size cohort exploration may include up to 30 patients for a total enrollment of up to 60 patients.

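### Section 11.2.3.1 reverses a local progression on any later shrinkage, even after non-surgical salvage to the index lesion, so control obtained by a second treatment can be credited to study FSRT

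*Combined protocol and SAP*

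**What the plan says.** Section 11.2.3.1 scores local control of the index lesion with three rules:

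- Imaging: "a 20% increase in maximal diameter from nadir represents local tumor progression".
- Surgery: "the presence of more than scant tumor cells present at the time of salvage surgery will be considered a local tumor failure".
- Reversal: an apparent increase in diameter that is "found to subsequently decrease in size upon further imaging will be considered an effect of therapy rather than a local failure".

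Table 8.1 requires brain MRI at baseline and at 1, 3, 6 and 12 months, in the row labelled "MRI brain (Local & CNS control per protocol/RANO-BM". Section 9.4 gives the same follow-up times, ending with "completion of the FACT-Br questionnaire at 1 month, 3 months, 6 months, and 12 months after completion of radiation treatment".

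Section 11.5.1 calls the analysis descriptive and exploratory, summarizes by dose level, and lists tumor response at each visit for each patient. If there are enough data, "local tumor control rate, central nervous system disease control rate and corresponding exact confidence interval will be calculated". On numbers, "Up to 10 evaluable patients may be enrolled at a specific dose prior to making a final dose escalation/de-escalation decision", and Section 11.6 adds "Each specific tumor size cohort exploration may include up to 30 patients for a total enrollment of up to 60 patients".

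**The concern.** The reversal rule asks only whether the lesion later became smaller. It does not ask by how much, or whether something other than study FSRT made it shrink. The surgical rule shows that salvage was foreseen, yet non-surgical salvage has no counterpart.

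Section 11.2.3 sets out to measure local control with FSRT, and the rationale for escalation (Sections 2.6 and 2.7) rests partly on better control at higher dose. A lesion that failed FSRT and responded to a second course of radiation is not evidence of control by FSRT. If it enters the numerator, the rate at that dose level mixes two treatments.

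**Working it through.** The documents give no target rate, power or sample size for local control, so there is no planned figure to reproduce. The check is a reading of the text followed by arithmetic for scale.

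**1. Does another section limit the clause?**

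- Section 7.2 has medications recorded and bars cytotoxic chemotherapy during FSRT. It does not mention salvage radiation and does not link any therapy to local-control scoring.
- Section 11.5.1 has no rule for salvage given before the rate is calculated.
- The RANO-BM table in Appendix B declares progression of target lesions at 20% or more over nadir and has no reversal rule for them. The reversal is the protocol's own addition.

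None of these limits it.

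**2. Literal application (example diameters are assumptions).**

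- *Salvaged lesion:* growth of at least 20% over nadir, repeat radiation to the lesion, then a smaller diameter. There was no surgery, so the histology rule does not apply. The later decrease triggers the reversal, and the lesion is scored as controlled.
- *Trivial shrinkage:* nadir 2.0 cm, so the threshold is 2.0 × 1.2 = 2.4 cm. Growth to 2.6 cm is 2.6/2.0 = 1.30, or +30%. A later 2.5 cm is 2.5/2.0 = 1.25, still +25%. The lesion remains past the threshold but is scored as controlled.

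**3. Opportunity.** Growth first seen at 1, 3 or 6 months has a later required MRI on which it can be reversed. Growth first seen at 12 months has none.

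**4. Size per patient.** One reclassified patient moves the rate by 1/n. Exact (Clopper-Pearson) 95% limits are the 0.025 quantile of Beta(x, n−x+1) and the 0.975 quantile of Beta(x+1, n−x). The counts are illustrative.

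| n | Before | After | Shift |
|---|---|---|---|
| 10 (one dose level) | 7/10 = 70% (34.8–93.3) | 8/10 = 80% (44.4–97.5) | 10 points |
| 30 (one size cohort) | 22/30 = 73.3% (54.1–87.7) | 23/30 = 76.7% (57.7–90.1) | 3.3 points |
| 60 (both cohorts) | 44/60 = 73.3% (60.3–83.9) | 45/60 = 75.0% (62.1–85.3) | 1.7 points |

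The plan summarizes by dose level, so the first row is the relevant one. Each shift is small against its interval.

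**5. Direction.** Let p be true control, q the share of controlled lesions with transient growth of at least 20%, s the share of those later seen to shrink, and r the share of true failures reversed.

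- Current rule: rate = p(1−q) + pqs + (1−p)r, so bias = (1−p)r − pq(1−s).
- Plain 20% rule, no reversals: bias = −pq.
- Salvage condition, if every reversed failure followed salvage: bias = −pq(1−s).

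Take p = 0.74, the retrospective 12-month figure for tumors of 2 cm or more in Section 2.5.1, where failure is not defined. The values of q, s and r are assumptions (0–20%, 30–100%, 0–25%).

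| q, s, r | Current rule | Plain rule | With salvage condition |
|---|---|---|---|
| 0.2, 0.3, 0 | −10.4 | −14.8 | −10.4 |
| 0.1, 0.5, 0.1 | 0.26×0.1 − 0.74×0.1×0.5 = −1.1 | −7.4 | −3.7 |
| 0.2, 0.3, 0.25 | 0.26×0.25 − 0.74×0.2×0.7 = −3.9 | −14.8 | −10.4 |
| 0, any, 0.25 | 0.26×0.25 = +6.5 | 0 | 0 |

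Bias is in percentage points. Over the assumed ranges the current rule runs from −10.4 to +6.5. Relative to the plain rule, the clause can only raise the rate. Relative to true control, its net bias can take either sign. The model leaves out treatment effect that is re-irradiated as presumed progression; the salvage condition would score that as failure and lower the rate further.

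**The case against.** The strongest reply is that the salvage reading is strained. The clause speaks of an apparent increase and an effect of therapy, under an endpoint about control with FSRT. Growth that prompts a second course of radiation is not naturally either, and nothing shows that the trial would score such a lesion as controlled. This stands as a statement of intent. But the word apparent is not defined, and the rule as written is triggered by any later decrease, so the outcome depends on who scores the lesion.

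Second, the planned listings of response by visit would show enlargement followed by decrease, so a reader could rebuild a rate without reversals. That also stands, and it narrows the gap. What the listings need not show is salvage radiation to the index lesion between the two scans.

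Third, a minimum decrease is a trade-off. Requiring return below the threshold could score treatment effect still resolving at the last MRI as failure. This is accepted, and the minimum decrease therefore belongs in a sensitivity analysis, not in the main rule.

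A reader might infer that the clause makes the reported control rate too high. The documents do not support that. The clause also correctly removes treatment effect, the frequencies are unknown, and under some assumptions the rate is too low with or without the change.

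Finally, Section 11.2.3.1 cites RANO-BM, whose full text was not available here beyond the Appendix B table, nor was the text between Sections 9.4 and 11.0. The gap is shown for the supplied text only.

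**Conclusion.** The point holds as a defect of attribution. Followed literally, Section 11.2.3.1 credits study FSRT with control of an index lesion that progressed, was salvaged without surgery and then shrank. It also counts as controlled a lesion that shrank trivially and is still at least 20% above nadir.

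The frequency cannot be derived from the documents. The only firm size is arithmetic: 10 points per reclassified patient at n=10. The range of −10.4 to +6.5 points for net bias rests on assumed q, s and r and on a retrospective 74%.

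A reader might also infer that dose-finding is compromised. It is not: the MTD rests on dose-limiting toxicity under the mTPI rule, and neither that decision nor the sample size uses local control. The endpoint is secondary and descriptive, with a rate and interval only if data allow. This is a cheap improvement of minor severity.

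**What to change.** This concerns endpoint scoring only and does not direct care.

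- Add one sentence to Section 11.2.3.1: growth is reclassified as treatment effect only if the later decrease occurs with no intervening non-surgical salvage directed at the index lesion (repeat stereotactic radiation, or whole brain radiation given for progression of that lesion).
- Leave the histology rule for salvage surgery as it is.
- Have the date, type and reason of any index-lesion salvage available when the endpoint is scored.
- Report two sensitivity rates: one with no reversals, and one that allows a reversal only on return to below 20% above nadir.

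Settle the wording before outcomes are scored, so that the choice cannot depend on results.

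The cost is one sentence, three data items per salvage and two derived rates. The reported rate may be lower, by 10 points per affected patient at n=10. Treatment effect that was re-irradiated as presumed progression stays a failure. In the middle scenario above, net bias moves from −1.1 to −3.7 points, so the case for the change is that the rate describes study FSRT alone, not that it is closer to true control.
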